6. TREATMENT OF SUBJECTS

All vaccines associated with this study are to be stored separately from other vaccines and medications in a secure location under appropriate storage conditions with temperature monitoring. **All vaccines associated with this study must be checked for expiration date prior to use. Expired vaccines must not be administered to subjects.**

6.1 Study Vaccine(s)

The term ‘study vaccine’ refers to those vaccines provided by the sponsor, which will be evaluated as part of the study objectives. The study vaccines specific to this study are described below.

Investigational vaccine: aH5N1

Six different formulations of the aH5N1 vaccine in 6 different HA/MF59 combinations will be tested in this study, see [Table 6.1](#). The full composition of the active vaccine components of the currently licensed adult formulation for aH5N1 (7.5 µg HA of H5N1 influenza strain combined with 0.25 mL MF59) is reported in [Table 6.2](#).

Table 6.1: H5N1 HA and MF59 content of the 6 vaccine formulations.

Arm*	H5N1 HA content	MF59 content**	Injection volume
A	1.875 µg	50% MF59	0.25 mL
B	3.75 µg	50% MF59	0.25 mL
C	7.5 µg	50% MF59	0.25 mL
D	1.875 µg	100% MF59	0.5 mL
E	3.75 µg	100% MF59	0.5 mL
F	7.5 µg	100% MF59	0.5 mL

* Approximately 70 subjects will be randomized per treatment arm, ie, 35 subjects in each age cohort.

**50% MF59 refers to half the standard MF59 content of the licensed adult formulation for H5N1.

Table 6.2: Full composition of the active vaccine components.

Composition of the active vaccine components	
Component	7.5 µg + 100% MF59 per 0.5 mL
Influenza virus surface antigens (HA and NA) A/turkey/Turkey/1/2005 (H5N1)-like (NIBRG-23)	~7.5-µg HA
% MF59 content relative to commercial vaccine	100%
Squalene	9.75 mg
Polysorbate 80	1.175 mg
Sorbitan trioleate	1.175 mg
Sodium citrate dihydrate	0.66 mg
Citric acid monohydrate	0.04 mg
Sodium chloride	[REDACTED]
Potassium chloride	[REDACTED]
Potassium dihydrogen phosphate	[REDACTED]
Disodium phosphate dihydrate	[REDACTED]
Magnesium chloride hexahydrate	[REDACTED]
Calcium chloride dihydrate	[REDACTED]
Water for injection	Up to 0.5 mL
Vaccine Presentation	Prefilled syringe
Volume of Component	~0.5 mL

Subjects will be randomized to receive 2 doses of study vaccine, 3 weeks apart, according to the vaccine group assignments shown in [Table 1](#).

6.2 Non-Study Vaccines

The term ‘non-study vaccine’ refers to those vaccines which will be intentionally given to study subjects but not formally included in the analysis of study objectives. No “non-study vaccines” will be given as part of this study.

Subjects are not prohibited from receiving other vaccinations during the course of the trial as long as these are not an influenza vaccination administered prior to visit 3 (Day 43). Please see [section 6.5](#) for further details. Following Day 43 other vaccines may be administered, including seasonal flu.

6.3 Vaccine Preparation and Administration

The investigator or designee will be responsible for oversight of the administration of vaccine to subjects enrolled in the study according to the procedures stipulated in this study protocol. The study vaccines will be administered only by unblinded personnel who are qualified to perform that function under applicable local laws and regulations for the specific study site.

The study vaccines will be supplied in kits (per subjects/per visit) containing the required materials to administer the specific formulation at the site. The kits may contain the following components, depending on the dose regimen:

- PFS, adjuvanted (50% MF59) H5N1 A/turkey/Turkey/1/2005 1.9 µg/0.25 mL
- PFS, adjuvanted (100% MF59) H5N1 A/turkey/Turkey/1/2005 1.9 µg/0.5 mL
- PFS, adjuvanted H5N1 (50% MF59) A/turkey/Turkey/1/2005 3.75 µg/0.25 mL
- PFS, adjuvanted (100% MF59) H5N1 A/turkey/Turkey/1/2005 3.75 µg/0.5 mL
- PFS, adjuvanted H5N1 (50% MF59) A/turkey/Turkey/1/2005 7.5 µg/0.25 mL
- PFS, adjuvanted (100%) H5N1 A/turkey/Turkey/1/2005 7.5 µg/0.5 mL

All formulations will be supplied as PFSs, depending on the treatment allocation 0.25 mL or 0.5 mL will be administered.

For detailed vaccine preparation and administration instructions unblinded personnel should refer to the IMP handling instructions.

PRECAUTIONS TO BE OBSERVED IN ADMINISTERING STUDY VACCINE:

Prior to vaccination, subjects must be determined to be eligible for study vaccination and it must be clinically appropriate in the judgment of the investigator to vaccinate. Eligibility for vaccination prior to first study vaccine administration is determined by evaluating the entry criteria outlined in protocol [sections 4.1, Inclusion Criteria](#) and [4.2, Exclusion Criteria](#).

Eligibility for subsequent study vaccination is determined by following the criteria outlined in [section 4.3, Criteria for Delay of Vaccination](#).

Eligibility for non-study vaccines should be determined by the investigator, pending the review of the package insert of the relevant vaccine and the guidelines described in [section 6.2, Non-Study Vaccines](#).

Study vaccines should not be administered to individuals with known hypersensitivity to any component of the vaccines.

Vaccine administration will be performed intramuscularly, anterolateral thigh for children ages <2 years; deltoid for children ages \geq 2 years, unless insufficient deltoid mass.

Standard immunization practices are to be observed and care should be taken to administer the injection intramuscularly. Before administering vaccine, the vaccination site is to be disinfected with a skin disinfectant (eg, 70% alcohol). Allow the skin to dry. **DO NOT inject intravascularly.**

As with all injectable vaccines, trained medical personnel and appropriate medical treatment should be readily available in case of anaphylactic reactions following vaccine administration. For example, epinephrine 1:1000, diphenhydramine, and/or other medications for treating anaphylaxis should be available.

6.4 Vaccine Administration Error or Overdose of Vaccine

Vaccine administration error is defined as receiving a dose of study vaccine that was not reconstituted as instructed or administered by a different route from the intended route of administration. An overdose of study vaccine (whether accidental or intentional) is defined when a dosage higher than the recommended dosage is administered in one dose of study aH5N1 vaccine.

An overdose would also occur if two doses of the study vaccine are administered within half the time of the recommended interval between doses, as defined in the protocol.

Any vaccine administration error or overdose of study vaccine detailed in this protocol must be reported as an adverse event, and if the vaccine administration error or overdose is associated with a serious adverse event, it must be reported as such within 24 hours to the sponsor or delegate.

6.5 Prior and Concomitant Medications and Vaccines

All medications, vaccines, including influenza vaccines (within the last 2 years), and blood products taken or received by the subject within 3 months prior to the start of the study are to be recorded on the prior and concomitant medications eCRF. See the exclusion criteria in [section 4.2, Exclusion Criteria](#) for details on medication that is not allowed prior and during the study.

The use of antipyretics and/or analgesic medications within 24 hours prior to vaccination must be identified and the reason for their use (prophylaxis versus treatment) must be described in the source document and concomitant medications eCRF. The use of antipyretics/analgesics within 24 hours prior to vaccine administration is a reason to delay study vaccination (see [section 4.3, Criteria for Delay of Vaccination](#)).

Medications taken for prophylaxis are those intended to prevent the onset of symptoms. Medications taken for treatment are intended to reduce or eliminate the presence of symptoms that are present.

Concomitant medications include all medications (including vaccines) taken by/administered to the subject at and after enrolment and must be documented on the concomitant medications eCRF. From Day 1 to Day 43 all concomitant medications should be recorded in the eCRF. In the follow-up period (Day 44 through Day 387), only concomitant medications associated with SAEs, NOCDs, AEs leading to vaccine and/or study withdrawal, and AESIs should be recorded in the eCRF.

When recording concomitant medications/vaccines, they should be checked against the study entry and continuation criteria in [section 4, Selection of Study Population](#) to ensure that the subject should be enrolled/continue in the study.

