5.1.2 Screening

After an individual has consented to participate in the study and informed consent/assent is signed, that individual will be given a unique screening number manually created by the investigator. The subject's unique screening number will be documented in the screening and enrolment log. The eligibility of the subject will be determined based on the inclusion and exclusion criteria listed in [section 4, Selection of Study Population](#) and evaluated during this screening procedure.

Screening procedures will include the following:

1. Demographic data will be collected from the subject, including: age and/or Date of Birth, sex, race, ethnicity).
2. Relevant Medical history will also be collected, including but not limited to any medical history that may be relevant to subject eligibility for study participation such as prior vaccinations, concomitant medications, and previous and ongoing illnesses or injuries. Relevant medical history can also include any medical history that contributes to the understanding of an adverse event that occurs during study participation, if it represents an exacerbation of an underlying disease/pre-existing problem.
3. Review of systems is a structured interview that queries the subject and/or parent(s)/LAR(s) as to any complaints the subject has experienced across each organ system. This will be performed before enrolment and used to guide physical examination. A general physical examination is to be performed by a qualified health care practitioner. “Qualified health care practitioner” refers to any licensed health care professional who is permitted by institutional policy to perform physical examinations and who is identified within the study staff signature log.
4. If applicable, prior and concomitant medications or vaccinations taken prior to start of study, including influenza vaccinations in the past 2 years, should be collected (refer to [section 6.5, Prior and Concomitant Medications and Vaccines](#) for further details).
5. Collection of clinical signs is to be performed: weight, height and body temperature. If body temperature is $\geq 38.0^{\circ}\text{C}$ ($\geq 100.4^{\circ}\text{F}$) at the time of screening, blood draw and/or vaccination must be postponed until 3 days after the fever has resolved (see [section 4.3, Criteria for Delay of Vaccination](#)).

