8.4.1 Analysis of Demographic and Baseline Characteristics

Descriptive statistics (mean, SD, median, minimum and maximum) for age, height, weight, and BMI at enrolment will be calculated overall, by vaccine group and age cohort.

Distributions of subjects by sex, race, ethnicity, country and previous influenza vaccination status will be summarized overall, by vaccine group and age cohort.

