8. GENERAL ISSUES FOR STATISTICAL ANALYSES

8.1 Adjustment for Covariates

The main statistical analysis includes descriptive statistics for the overall population <9 years of age. Subgroup analyses will be done by age cohort (6 months to < 36 months, 3 to < 9 years). Summary tables will show unadjusted GMTs for each vaccine group by assessment.

Adjusted GMTs will be calculated based on the log-transformed antibody titers at Day 22 and Day 43 using an Analysis of Covariance (ANCOVA) model which includes the log-transformed pre-vaccination antibody titer, age cohort and vaccine group.

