10.1 Demographics

Age, height, weight and body mass index will be summarized by reporting the mean, standard deviation, median and range, and will be calculated by vaccine group and overall.

In addition, the frequency of age categories will be reported as 6 to < 36 months and 3 to < 9 years (age cohort). The number and percentages of subjects by sex, country, ethnic origin, race, and previous influenza vaccine (within the past 2 years) will be presented by vaccine group and overall.

Demographic data will be tabulated for the All Enrolled, FAS, PPS and Safety sets.

The distribution across all stratification factors (site*age subgroup) will be presented by vaccine group and overall. This table will be presented based on the IRT data and – if different – also for the actual CRF data.

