The analysis model for the GMT will be done using a general linear model on log-transformed (base 10) Day 22 or Day 43 titers as the outcome variable and as covariates: formulation, log-transformed pre-vaccination titer and age subgroup. From this model, adjusted differences in the least square means (on the log scale) will be produced with 95% confidence limits for each formulation versus the standard formulation F with highest dose. The estimated difference and the confidence limits will be back-transformed to obtain an *adjusted GMT ratio* with 95% confidence limits.

Potential interaction between age stratum and treatment effect will be examined by including an interaction term in the model and present the results of the overall interaction test. The analysis will also be done for each age subgroup separately.

Geometric Mean Ratios (GMRs)

Summary statistics (geometric mean, Coefficient of variation, minimum, median, maximum) of the relative increase in titers will be presented by assessment (Day 22 and Day 43) and vaccine group overall and by age subgroup.

The analysis model for the GMR in titers will be done using the same models as mentioned on log-transformed (base 10) (Day 22 titers/Day 1 titers and Day 43 titers/Day 1 titers) as the outcome variable excluding the pre-vaccination titer as covariate.

Analysis of binary endpoints

The number and proportion of subjects achieving the binary endpoints (seroconversion or titer \geq 1: 40) will be summarized by assessment (Day 22 and Day 43) and vaccine group overall and by age subgroup. These summaries will be reported together with the associated two-sided 95% confidence intervals for the proportion according to Clopper-Pearson.

Statistical Analysis Plan, Protocol Number V87_30

06 MAY 2022 Final Version 1.0

The binary endpoints (i.e. percentage of subjects with seroconversion or with titer $\geq 1:40$) will be compared between each of formulations versus formulation F (highest dose) expressed by the differences of proportions with 95% CI using the Miettinen and Nurminen method without adjustment for the age stratum.

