11.4 Exploratory Objectives Analysis

A *post hoc* decision will be made if other measurements will be made. If adequate sera are available and depending on assay availability, antibody responses and their persistence to seasonal and/or homologous and/or heterologous pandemic influenza strains as measured by HI, MN and SRH assays may be described at Days 1, 22, 43, and 202 in the same manner as for primary and secondary immunogenicity endpoints. The results will be included in a separate report. An additional exploratory analysis will be conducted making use of the factorial design of the study and assess the impact of the different factors (dose of MF59 and amount of antigen) on the titers and their GMT. For that we use an analysis of covariance model on log transformed (base ten) Day 22 or Day 43 HI (or MN) titers as the outcome variables and terms for covariates: age cohort, dose of MF59 adjuvant, amount of antigen and Day 1 pre-vaccination HI (or MN) titer. Potential covariate interaction effects will also be examined in this model.

Statistical Analysis Plan, Protocol Number V87_30

06 MAY 2022 Final Version 1.0

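### Influenza vaccination in the past 2 years is recorded and tabulated but enters no titre model; pre-specifying it as a covariate could bring a small gain in precision

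*Protocol*

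**What the plan says.** **Collection.** Protocol 6.5 asks for "All medications, vaccines, including influenza vaccines (within the last 2 years), and blood products taken or received by the subject within 3 months" before the start of the study. Protocol 5.1.2 repeats the longer window at screening: prior products, "including influenza vaccinations in the past 2 years, should be collected".

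**Planned use.** The variable appears only in baseline tables. Protocol 8.4.1 lists it with sex, race, ethnicity and country. SAP 10.1 says that "previous influenza vaccine (within the past 2 years) will be presented by vaccine group and overall".

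**Titre models.**
- SAP 8.1: adjusted GMTs come from an ANCOVA "which includes the log-transformed pre-vaccination antibody titer, age cohort and vaccine group".
- SAP 11.2: the GMT model has "as covariates: formulation, log-transformed pre-vaccination titer and age subgroup". It yields ratios of A to E against F, overall and in each age cohort. The GMR model is the same without the pre-vaccination titre.
- SAP 11.3: Day 202 is analysed in the same way.
- SAP 11.4: the factorial model has "terms for covariates: age cohort, dose of MF59 adjuvant, amount of antigen and Day 1 pre-vaccination HI (or MN) titer".

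Prior influenza vaccination is also not a stratification factor (site and age cohort, SAP 4.1) and not one of the GMT subgroups (sex, country and site, besides age cohort, SAP 8.5).

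**The concern.** The only individual measure of immune status in the GMT models is the Day 1 titre against H5N1, and it may carry little information. The documents describe people as having no prior immunity to a pandemic strain (SAP 1), exclude children who have had an H5N1 vaccine (Protocol 4.2), and set every value below the quantification limit to half that limit (SAP 8.7). If most children share one Day 1 value, that covariate cannot absorb a chance difference between arms in anything else. The GMR model has no individual immune covariate at all.

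If children vaccinated against influenza in the past 2 years respond differently to H5N1 vaccine, two things follow. The residual variance is larger than it need be. A chance difference between arms in the share vaccinated also stays in the estimated ratio, and an imbalance in F enters all five ratios. The effect is larger in the analyses by age cohort, where about 30 evaluable children per arm are expected.

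**Working it through.** **Inputs from the documents** (SAP 5): SD of log10 HI titre 0.7; at least 60 evaluable per arm and 30 per arm and cohort (70 × 0.86 = 60.2; 35 × 0.86 = 30.1).

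**Assumptions, not in the documents:** share previously vaccinated p = 0.2 to 0.5; difference in mean titre between vaccinated and unvaccinated children d = 0.1 to 0.4 log10, a titre ratio of 10^0.1 = 1.26 to 10^0.4 = 2.51.

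**Step 1: the plan's own figures.** The interval factor for one GMT is 10^(±1.96 × 0.7/√n). It gives 0.56 to 1.78 at n = 30 and 0.67 to 1.50 at n = 60, as stated. The stated 80% power for a ratio of 2.5 at n = 60 does not reproduce: the normal approximation gives 87.6% and the t-test 87.0% (two-sided 0.05). The stated figure is conservative, and this does not affect the point here.

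**Step 2: interval factor for a ratio to F**, 10^(1.96 × 0.7 × √(2/n)):
- n = 60: 10^0.2505 = 1.78
- n = 30: 10^0.3542 = 2.26

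**Step 3: variance explained by the covariate**, p(1−p)d²/0.7²:
- p = 0.2, d = 0.1: 0.16 × 0.01/0.49 = 0.33%
- p = 0.5, d = 0.4: 0.25 × 0.16/0.49 = 8.2%

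**Step 4: narrowing of the interval on the log scale**, 1 − √(1 − variance explained): 0.2% to 4.2%. At the upper end the ratio's interval factor falls from 1.78 to 10^(0.2505 × 0.958) = 1.74 at n = 60.

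**Step 5: shift in a ratio to F from a 2-SD chance imbalance.** The SD of the difference in shares is √(2p(1−p)/n), and the shift is 10^(2 × SD × d).

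| | n = 60 (overall) | n = 30 (one cohort) |
|---|---|---|
| Imbalance SD, p = 0.2 | 0.073 | 0.103 |
| Imbalance SD, p = 0.5 | 0.091 | 0.129 |
| Shift, p = 0.2, d = 0.1 | 1.03 | 1.05 |
| Shift, p = 0.5, d = 0.4 | 1.18 | 1.27 |
| Planned interval factor of the ratio | 1.78 | 2.26 |

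The SD formula assumes simple randomisation. If vaccination rates differ by site, stratification by site and age balances part of that variation, so these shifts are upper figures.

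**Step 6: bias and coverage by simulation.** The setting was six arms of 30 in each of two cohorts, 3% with a detectable Day 1 titre, 30% and 50% previously vaccinated in the two cohorts, and 4,000 runs for each assumed titre ratio of 1.5, 2 and 3. The planned ANCOVA gave a mean log10 ratio within 0.003 of the true value of zero and coverage of 94.7% to 95.7%. With the covariate added, coverage was 95.0% to 95.7%. Omitting the covariate changed the ratio within a single trial over these 95% ranges:
- titre ratio 1.5: 0.92 to 1.09
- titre ratio 2: 0.88 to 1.14
- titre ratio 3: 0.83 to 1.22

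**The case against.** The strongest reply is that the premise lies outside the documents. Neither document says that influenza vaccination changes the H5N1 response, and neither gives an effect size or the share of children vaccinated. That stands, and it makes the whole point conditional.

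The second reply is that chance imbalance in an unadjusted factor is ordinary sampling variation. The SD of 0.7 already contains it, so the planned intervals already allow for it. That also stands. A reader might infer that the ratios to F are biased or their intervals too narrow. Randomisation rules out the first, and the simulation shows correct coverage.

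Three further inferences go beyond the text:
- **That the Day 1 titre is known to be nearly constant.** This is reasonable for HI but remains an inference. No baseline distribution is given, SAP 8.7 gives no numerical MN limit, and the seroconversion definitions provide for detectable baselines.
- **That the 2-year item is the only record of earlier priming.** Protocol 3.4.1 lists vaccination history including influenza vaccination with no time limit, and Protocol 5.1.2 collects prior vaccinations and illnesses as medical history.
- **That the longer look-back, or the limits on vaccination before Day 43, mark this history as an expected covariate.** Sex, race, ethnicity and country are tabulated in the same way and are also outside the main models. Limits on vaccination during the study say nothing about earlier history.

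The plan also handles part of the matter. Randomisation is stratified by site and age, age cohort is in the models, GMTs are shown by country and site, and the baseline table will reveal an imbalance. It names no response to one, however, and adjusting only after seeing it would be post hoc.

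Finally, the study is descriptive and the choice of covariates is discretionary. That limits the weight of the point but is no reason against a change that costs almost nothing.

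**Conclusion.** The point holds as an inexpensive improvement, not as an error in the plan. The variable is collected and tabulated, yet absent from every titre model, stratum and GMT subgroup.

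The gain exists only if recent influenza vaccination is prognostic for H5N1 titre. Even at the favourable end of the assumed ranges, intervals narrow by about 4%. The largest 2-SD shift (1.18 overall, 1.27 within a cohort) sits well inside the ratio's own interval factor (1.78 and 2.26). At the other end of the ranges the gain is negligible.

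The sizes rest on the assumed 20-50% vaccinated, the assumed 0.1-0.4 log10 effect, and an SD that SAP 5 takes from studies in healthy elderly people.

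**What to change.** Before unblinding, amend the SAP to add influenza vaccination within the past 2 years (yes/no) as a covariate in:
- the log10 GMT and GMR models of SAP 11.2, overall and by age cohort, which SAP 11.3 carries to Day 202;
- the factorial model of SAP 11.4, overall and by age cohort.

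Align the covariate list in SAP 8.1, and state how an unknown history is coded. Keep the unadjusted GMTs as planned. Describe the change as a precision gain that may be small, not as correction of a bias.

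The cost is a short SAP edit and one degree of freedom per model, with no new data collection. If the team prefers to leave the main models alone, a pre-specified sensitivity ANCOVA with this covariate, or a stated reason for omitting it, would also answer the point.
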